## 6.3.10 Protocol Deviations and Analysis Populations

All protocol deviations will be recorded by the Investigator, incorporated to the mapped (SDTM) database and will be listed by subject number [Listing 16.2.2.1].

Assignment to analysis populations and data exclusions for individual assessments and time points will be listed by subject number for the safety analysis population [Listing 16.2.3.1].

## 6.3.11 Demographic Data and Baseline Data

### 6.3.11.1 Demographics

Demographics and baseline characteristics including date of informed consent, date of birth, age at informed consent date, sex, race, ethnicity, screening height, weight and BMI will be listed for the safety analysis population [Listing 16.2.4.1]. Age, sex, race, ethnicity, and screening height, weight and BMI will be summarized by treatment and overall for the safety analysis population [Table 14.1.2.1].

### 6.3.11.2 Hamilton Depression Scale (HAM-D)

The HAM-D total score and item scores from site and central raters will be listed for all screened patients [Listing 16.2.4.2.1]. HAM-D total score at Visits 1, 1.1 and 2.1 for screening will be summarized by treatment and overall for the Intent to Treat Population [Table 14.1.2.2]. It will be noted that the qualifying HAM-D total scale was changed in CSP amendment 4 from HAM-D  $\geq 21$  to HAM-D  $\geq 18$  and Visit 1 and 1.1.

# Statistical Analysis Plan

Taisho Pharmaceutical R&D Inc.  
Protocol TS121-US201

Statistical Analysis Plan (SAP)

Final 2.0  
18 Dec 2018  
CONFIDENTIAL

## ***6.3.11.3 Baseline Major Depressive Disorder Characteristics***

Major depressive episode records from medical history will be listed with the calculated duration (months) of current depressive episode and duration from first MDD Diagnosis (years) [Listing 16.2.4.2.2] and presented in a summary table for the intent to treat population [Table 14.1.3]. The summary table will also present baseline MADRS total score and baseline HAM-A total score.

## ***6.3.11.4 Medical and Psychiatric History***

Any findings for medical and psychiatric history will be coded using MedDRA Version 19.1 and will be listed by subject number for the safety analysis population. MedDRA system organ class (SOC) and preferred term (PT) where a condition or abnormality has been reported, will be listed for the safety analysis population [Listing 16.2.4.3].

Medical history and psychiatric history will be presented in summary tables by treatment group and overall by SOC and PT for the safety analysis population [Table 14.1.4].

## ***6.3.11.5 Concomitant Medication***

All concomitant medications for patients in the Safety Analysis Population will be listed with the identification number of any associated medical history or adverse event for the safety analysis population [Listing 16.2.4.4]. Prior and concomitant ADTs will be included in this listing and also listed separately [Listing 16.2.4.5]. The record of medications includes reported medication and WHO-DD preferred term. Concomitant medications and indications will be summarized by preferred term by treatment group and overall for the safety analysis population [Table 14.1.5]. Duration of current ADT will be summarized with baseline MDD characteristics [Table 14.1.3].

## ***6.3.11.6 Screening Laboratory Tests***

Drug screening [Listing 16.2.4.6.1], screening serology [Listing 16.2.4.6.2] and pregnancy test results [Listing 16.2.4.6.3] will be listed for the safety analysis population.

# Statistical Analysis Plan

Taisho Pharmaceutical R&D Inc.  
Protocol TS121-US201

Statistical Analysis Plan (SAP)

Final 2.0  
18 Dec 2018  
CONFIDENTIAL

## 6.3.12 Study Drug Exposure and Pharmacokinetic Concentration Data

### 6.3.12.1 Exposure to the Investigational Medicinal Product

The record of dose compliance through the placebo lead-in period and treatment period will be listed [Listing 16.2.5.1] and summarized [Table 14.2.1] for the safety analysis population.

### 6.3.12.2 Pharmacokinetic Concentrations

The individual plasma concentration of [REDACTED], the date and time of last preceding dose, actual sampling date and elapsed time will be listed for the PK analysis population [Listing 16.2.5.2].

Plasma [REDACTED] concentrations will be presented in a scatter plot figure representing concentration versus actual elapsed time post dose and different symbols for TS-121 10 mg or TS-121 50 mg treatment groups [Figure 14.2.1] for the PK analysis population.

#### Handling of Values Below the Lower Limit of Quantification (BLQ)

All concentrations BLQ or missing data will be labeled as such in the concentration data listings. The lower limit of quantification (LLOQ) will be reported in a listing footnote.

- All BLQ values will be substituted by zeros in the figures.

#### Significant Digits

Individual drug concentrations values are reported with 3 significant digits.

## 6.3.13 Efficacy Analysis

### 6.3.13.1 Primary Endpoint

The Montgomery-Asberg Depression Rating Scale (MADRS) total score with change from baseline will be listed by subject number [Listing 16.2.6.1.1]. A descriptive statistics summary table will be presented for MADRS total score and total score change from baseline by treatment and visit [Table 14.2.2.1]. Baseline for calculating total score change will be the Visit 3 assessment. Each MADRS item will be listed by subject number [Listing 16.2.6.1.2] and MADRS item frequency counts will be presented in a summary table by treatment and visit [Table 14.2.2.2] for the Intent to Treat Population.

# Statistical Analysis Plan

Taisho Pharmaceutical R&D Inc.  
Protocol TS121-US201

Statistical Analysis Plan (SAP)

Final 2.0  
18 Dec 2018  
CONFIDENTIAL

Treatment group mean (+/- SE) MADRS total score and total score change from baseline will be plotted versus treatment [Figure 14.2.2.1 and Figure 14.2.2.2].

To evaluate the efficacy of TS-121 compared to placebo on MDD symptoms as measured by the MADRS scale, Mixed Model Repeated Measures analysis (MMRM)/non-parametric methods will be used to compare the difference between the three treatment groups on the primary endpoint (change from baseline in MADRS score) depending on the distribution of the data. The baseline MADRS total score will be included as a covariate. Comparisons of TS-121 10 mg versus placebo and TS-121 50 mg versus placebo will be evaluated at each timepoint.

The following is example SAS programming code that will be used to fit the MMRM model and evaluate treatment mean differences:

```
Proc Mixed Method = REML;  
    Class GROUP Subject_ID VISIT;  
    Model Change = Baseline GROUP VISIT GROUP*VISIT  
        / solution ddfm=kenwardroger;  
    repeated VISIT / sub=Subject_ID type= UN;  
    lsmeans GROUP*VISIT / pdiff alpha=0.05 cl;  
    ods output lsmeans=lsm covparms=cp tests3=t3 diffs=diffs;  
  
run; quit;
```

In case the repeated measures model with unstructured covariance matrix (type = UN) fails to converge then the compound symmetry model (type = CS) will be used.

Least squares treatment group mean differences with 95% confidence intervals will be reported for TS-121 10 mg versus placebo and for TS-121 50 mg versus placebo evaluated at Visits 4, 5, 6/EOT and 7. The primary endpoints for analysis are treatment mean differences at Week 6/EOT [Table 14.2.2.3]. Statistical significance of Type 3 tests and model variance terms will be reported separately [Table 14.2.2.4].

The primary analysis will assess treatment mean differences at Week 6/EOT. An assessment of time on treatment will be performed as an analysis of covariance on the latest assessment of the primary endpoint, change in MADRS score. The model will include all patients in the specified population and may include patients with the baseline assessment and no post-baseline efficacy data. In this model, where TIME will be included as a continuous predictor in this model, a

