8.4 Duration of Patient Participation

This study is comprised of a screening period of up to 28 days, a 2-week placebo lead-in, a 6-week treatment period and up to 2-weeks for a follow-up visit. Eligible patients will be entered into a 2-week placebo lead-in at Visit 2, and if all entry criteria are met, randomized at Visit 3. Patients will remain in the treatment period of the study until Visit 6, and will return for a follow-up visit at Visit 7. Patients will participate in the study for approximately 3 months.

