10.5.2 Efficacy Analysis

10.5.2.1 Primary Endpoint

To evaluate the efficacy of TS-121 compared to placebo on MDD symptoms in MDD patients, Mixed Model Repeated Measures analysis (MMRM)/non-parametric methods will be used to compare the difference between the three treatment groups on the primary endpoint (change in MADRS score) depending on the distribution of the data. On the primary endpoint (change in MADRS score), as assessed at Week 6, a statistically significant GROUP*TIME interaction effect, with greater reductions in MADRS scores in the TS-121 groups, will be interpreted as indicating efficacy (GROUP: Placebo, TS-121 10 mg and TS-121 50 mg, TIME: Week 2, Week 4 and Week 6).

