# Statistical Analysis Plan

Taisho Pharmaceutical R&D Inc.  
Protocol TS121-US201

Statistical Analysis Plan (SAP)

Final 2.0  
18 Dec 2018  
CONFIDENTIAL

The following example SAS programming multiple imputation (MI) code will be used to assess pattern of missing visits:

```
Proc MI Nimpute=0;  
    Var GROUP TRT10 TRT50 BASE WEEK2 WEEK4 WEEK6 FOLLOW;  
run;
```

The indicator variables TRT10 (1 for TS-121 10 mg and otherwise 0) and TRT50 (1 for TS-121 10 mg and otherwise 0) are equivalent to the GROUP treatment classification variables.

The following MI code will be used to create a set of imputation data sets.

```
Proc MI Seed=xxxxx Nimpute=x out=impute_1 round= . . . .1 .1 .1 .1 ;  
    EM INITIAL = AC MAXITER=25 CONVERGE=0.00001;  
    Var TRT10 TRT50 BASE WEEK2 WEEK4 WEEK6 FOLLOW;  
run;
```

The number of imputed data sets (Nimpute) will be set to have relative efficiency > 95% for each imputed variable. This number is expected to be < 10.

The MMRM of Section 6.3.13.1 is then run by imputation number to generate two data sets: The model parameters (solutionF, solution for model fixed effects) and the treatment by visit mean differences. Only the set of treatment mean differences used to evaluate the Week 6/EOT treatment mean differences (GROUPDIF1-GROUPDIF2: D50-placebo, D10-placebo, D50-D10) will be sorted by GROUPDIF1, GROUPDIF2 and imputation number.

The following example SAS programming code will be used to evaluate the Week 6/EOT treatment mean differences (D50-placebo, D10-placebo, D50-10):

```
Proc Mianalyze Data=Diff(keep=GROUPDIF1 GROUPDIF2 Est_diff SE_diff) Edf=xx;  
    By GROUPDIF1 GROUPDIF1;  
    Modeleffects Est_diff;  
    Stderr SE_diff;  
    Ods Output Parameterestimates=Est_diff1 VarianceInfo = SE_diff1;  
run;
```

The following example SAS programming code will be used to evaluate the solution for model fixed effects.

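### The primary MMRM fits one baseline slope across all four visits, so the Week 6 contrast may be adjusted with a slope that is not the Week 6 slope

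*SAP*

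**What the plan says.** The example code in SAP 6.3.13.1, which the SAP says will be used, has "Model Change = Baseline GROUP VISIT GROUP*VISIT" as its model line. Baseline is not in the CLASS statement, so it enters as one continuous term with one coefficient. The text agrees with the code: "The baseline MADRS total score will be included as a covariate", with no mention of a visit-specific effect. The covariance is unstructured, "repeated VISIT / sub=Subject_ID type= UN", with compound symmetry as the fallback.

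Least squares mean differences are reported "evaluated at Visits 4, 5, 6/EOT and 7", so four visits share the slope. The primary contrast is at one of them: "The primary endpoints for analysis are treatment mean differences at Week 6/EOT".

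SAP 6.3.13.2 applies the same method to CGI-S, HAM-A and SDQ. For the multiple-imputation sensitivity analysis, SAP 6.3.13.3 states: "The MMRM of Section 6.3.13.1 is then run by imputation number".

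Visit 7 is off treatment (Protocol 8.4: "Patients will remain in the treatment period of the study until Visit 6, and will return for a follow-up visit at Visit 7"), and Protocol 10.5.2.1 defines the time factor without it: "TIME: Week 2, Week 4 and Week 6".

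**The concern.** The model is flexible where it need not be restrictive, with one exception. Each visit has its own treatment effect, variance and covariances, but the relation between baseline and change is held constant, and no reason is given. In a repeated-measures fit the common slope is a weighted combination of the visit slopes, and the weights come from the residual covariance, not from which visit is primary. The Week 6 contrast can therefore be adjusted with a slope set almost entirely by Week 2.

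The stakes are the Week 6 point estimate and its precision. SAP 5 and Protocol 10.1 state that the sample size does not rest on a power calculation, and both documents describe a pilot meant to estimate the effect size, so the estimate is the main product. Protocol 6.2 names no stratification factor, and entry depends on HAM-D rather than MADRS. Baseline MADRS balance is therefore left to chance and to this covariate.

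**Working it through.** The plan states no figure to reproduce. From the documents come the model, the four visits and 60 patients per arm (Protocol synopsis). All SDs, correlations, the 4-point difference used for power and the missing-data rate are assumptions.

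**1. Slope of change on baseline at visit t.** b_t = r_t × SD_t / SD_0 − 1. A falling correlation r_t makes it more negative; a rising SD_t makes it less negative. With SD_0 = 5, r = 0.50 and SD 7 at Week 2 give 0.50 × 7/5 − 1 = −0.30. At Week 6, r = 0.39 and SD 9 give 0.39 × 9/5 − 1 = −0.30. The correlation has fallen, yet the slopes are equal. The direction therefore cannot be known in advance.

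**2. Common slope.** β = 1′S⁻¹b / 1′S⁻¹1, where S is the residual covariance given baseline. Two worked cases use SD_0 = 5.5 and residual correlation 0.7 per visit step (AR-type):

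- Falling correlation: r = 0.60, 0.45, 0.35, 0.30 and SD = 7, 8.5, 9.5, 10. The slopes are −0.236, −0.305, −0.395, −0.455. The weights are 0.886, −0.056, 0.012, 0.158, so β = −0.269. At Week 6 the gap b_6 − β is −0.127: under-adjusted.
- Constant correlation: r = 0.45 and SD = 6.5, 8, 9.5, 10. The slopes are −0.468, −0.345, −0.223, −0.182. The weights are 0.763, 0.046, −0.005, 0.197, so β = −0.408. The gap is +0.185: over-adjusted.

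In both cases Week 6 itself carries a weight of about zero.

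**3. Conditional shift.** With complete data, the contrast using β differs from the correctly adjusted one by (b_6 − β) × baseline imbalance. One SD of chance imbalance is 5.5 × √(2/60) = 1.00 point (0.91 if SD_0 = 5).

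**4. Standard error.** The variance is (2/n)[S_66 + (b_6 − β)² SD_0²] with the common slope and (2/n)S_66 with Baseline*VISIT.

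- Falling correlation: S_66 = 9.5² × (1 − 0.35²) = 79.19, so √(79.19/30) = 1.625. Adding 0.127² × 5.5² = 0.49 gives √(79.68/30) = 1.630.
- Steep fall (Week 6 r = 0.25): S_66 = 9.5² × (1 − 0.25²) = 84.61, so the SE is 1.679. Adding 0.441² × 5.5² = 5.88 gives √(90.49/30) = 1.737.

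| Assumed pattern | Week 6 slope | Common slope | Shift per 1 SD imbalance | SE with term → without | SE inflation | Power at 4 points, with → without |
|---|---|---|---|---|---|---|
| Equal slopes | −0.49 | −0.49 | 0 | 1.171 → 1.171 | 0% | 92.7% → 92.7% |
| Falling correlation | −0.40 | −0.27 | −0.13 | 1.625 → 1.630 | 0.3% | 69.2% → 69.0% |
| Steep fall, residual correlation 0.7 | −0.57 | −0.19 | −0.38 | 1.679 → 1.722 | 2.5% | 66.3% → 64.2% |
| Steep fall, residual correlation 0.85 | −0.57 | −0.13 | −0.44 | 1.679 → 1.737 | 3.4% | 66.3% → 63.4% |
| Constant correlation, rising SD | −0.22 | −0.41 | +0.19 | 1.549 → 1.560 | 0.7% | 73.3% → 72.7% |
| Flattest at Week 6, steep again off treatment | −0.14 | −0.45 | +0.32 | 1.502 → 1.535 | 2.2% | 75.9% → 74.1% |

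A deliberately extreme corner (gap 0.5, baseline SD 7, Week 6 residual SD 9) gives √(1 + 0.25 × 49/81) = 1.073, that is 7% on the SE and about 6 power points.

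**5. Bias.** Four patterns were simulated (the falling correlation, both steep falls and the last row), with 600 trials each, a true difference of 0, and about 14% missing at Week 6 with more dropout on active drug. The mean Week 6 estimate was −0.08 to 0.05 with the common slope and −0.13 to 0.05 with Baseline*VISIT (Monte Carlo SE about 0.07). The difference between the two estimates, regressed on baseline imbalance, had slopes −0.15, −0.38, −0.43 and +0.32, close to the gaps behind the table. The empirical SD was larger with the common slope in the two steep-fall cases (1.866 against 1.827; 1.769 against 1.718) and no different in the other two.

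**6. Visit 7.** Dropping it moves the common slope by at most 0.06. In the falling-correlation case it goes from −0.269 to −0.254, slightly further from the Week 6 value.

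**The case against.** The strongest reply is that nothing here is an error. A baseline main effect is a valid prespecified adjustment, the code matches the text, and randomisation protects the contrast. The likely shift is a fraction of a point against an SE of about 1.5 to 1.7. All of that stands, and it limits the weight of the point.

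Three stronger readings are tempting, and the documents do not support them.

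- A reader might infer that the Week 6 contrast is under-adjusted. That requires the baseline correlation to fall steeply enough to outweigh the rise in SD. With a constant or slowly falling correlation the model over-adjusts, and with equal slopes there is no error. The documents give no MADRS SD or correlation.
- A reader might blame the off-treatment follow-up visit. Step 6 shows that it is not the main driver, and in the falling-correlation cases including it helps slightly. The difference between the visits in SAP 6.3.13.1 and the time factor in Protocol 10.5.2.1 is a separate matter of consistency.
- A reader might infer bias. None is expected under randomisation, and none was seen.

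It can also be said that the supplementary analysis of covariance in SAP 6.3.13.1 has a baseline slope not pooled over visits, because it uses one assessment per patient. True, but it takes the latest assessment, which need not be Week 6, and adds a GROUP*TIME term with continuous time. It is a different model and does not replace the primary contrast.

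**Conclusion.** The point holds as a small specification improvement. The primary MMRM may adjust the Week 6 difference with a baseline slope that is not specific to Week 6, in a direction the documents cannot settle. With baseline SD 5 to 5.5 and 60 per arm, the cost is 0 to about 0.4 MADRS points per 1-SD chance baseline imbalance, 0 to about 3% on the SE, and at most about 3 power points at an assumed 4-point difference. These sizes rest wholly on assumed variances and correlations, and zero is inside every range.

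The multiple-imputation analysis gives no check on this. Its imputation step treats baseline and each visit as joint variables, so each visit has its own relation to baseline, but the single-slope MMRM is then fitted to the completed data.

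**What to change.** In SAP 6.3.13.1, change the model line to: Model Change = Baseline GROUP VISIT GROUP*VISIT Baseline*VISIT. Amend the sentence on the baseline covariate to say that its effect may differ by visit. Make the same change for CGI-S, HAM-A and SDQ, and for the MMRM run on the imputed data in SAP 6.3.13.3. There, the MIANALYZE step for the fixed effects also needs the added term. The LSMEANS statement stays as it is.

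The cost is one model term and 3 degrees of freedom (four slopes instead of one), with no new data. It should be specified before database lock, so that it cannot later be seen as a post hoc covariate choice. Separately, one sentence should reconcile the visits in this model with the time factor in Protocol 10.5.2.1.

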## 6.3.2 Statistical Significance Level

Any statistical test or confidence interval (CI) will be two-sided and will be performed at the 5% level of significance, unless otherwise stated. No adjustment for multiple comparisons will be performed for calculation of CI or statistical significance.

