# Statistical Analysis Plan

Taisho Pharmaceutical R&D Inc.  
Protocol TS121-US201

Statistical Analysis Plan (SAP)

Final 2.0  
18 Dec 2018  
CONFIDENTIAL

for HAM-A total score and total score change from baseline (n, mean, SD, SE, CV%, minimum, median and maximum) by treatment and visit [Table 14.2.4.1]. A summary table will be presented for each item response of HAM-A, with score frequencies and the mean and median scores [Table 14.2.4.2]. Treatment group mean (+/- SE) HAM-A observed and change from baseline will be plotted versus treatment [Figure 14.2.4.1 and Figure 14.2.4.2].

Symptoms of Depression Questionnaire (SDQ) total score, total score change from baseline and item scores will be listed [Listing 16.2.6.4]. A descriptive summary table will be presented of total score observed and change from baseline results [Table 14.2.5.1] and a summary table of each item with the mean and median scores [Table 14.2.5.2]. Treatment group mean (+/- SE) SDQ total score and change from baseline will be plotted versus treatment [Figure 14.2.5.1 and Figure 14.2.5.2].

With respect to the secondary qualitative outcome variables, the MMRM/non-parametric methods described above will also be used to compare the difference among the three treatment groups for each secondary endpoint depending on the distribution of the data.

Changes from Baseline (Visit 3) to Week 6/EOT will be assessed for the following:

- CGI-S score [Table 14.2.3.3 LSmeans, Table 14.2.3.4 Type 3 tests]
- HAM-A total score [Table 14.2.4.3 LSmeans, Table 14.2.4.4 Type 3 tests]
- SDQ score [Table 14.2.5.3 LSmeans, Table 14.2.5.4 Type 3 tests]

The Pearson Chi-square test will be used to compare the difference between active treatment groups and the placebo group for the following secondary endpoints evaluated at Week 6/EOT. The 95% confidence interval (asymptotic calculation) for each treatment difference, TS-121 - Placebo, of percentage responders will also be reported.

- Percentage of MADRS responders ( $\geq 50\%$  reduction in total score) [Table 14.2.2.6]
- Percentage of CGI-I improvers (“Very much improved” or “Much improved”) [Table 14.2.3.2]

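### If the unstructured MMRM does not converge, the SAP drops straight to compound symmetry, which may misstate the Week 6 standard error in either direction

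*SAP*

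**What the plan says.** SAP 6.3.13.1 models change from baseline in MADRS total score with baseline, group, visit and group by visit. The covariance is specified as "repeated VISIT / sub=Subject_ID type= UN" and inference as "solution ddfm=kenwardroger", that is, model-based standard errors with the Kenward-Roger adjustment. The only provision for failure is that, if the unstructured model "fails to converge then the compound symmetry model (type = CS) will be used". No intermediate structure is named, and the code has no empirical standard error option.

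Treatment differences are "evaluated at Visits 4, 5, 6/EOT and 7", so four post-baseline visits, including the off-treatment follow-up, share the model. The contrast that matters is Week 6: "The primary endpoints for analysis are treatment mean differences at Week 6/EOT". Under SAP 6.3.2, tests and intervals "will be two-sided and will be performed at the 5% level of significance, unless otherwise stated".

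The model is reused elsewhere. For change in CGI-S, HAM-A and SDQ, SAP 6.3.13.2 says that "the MMRM/non-parametric methods described above will also be used to compare the difference among the three treatment groups". SAP 6.3.13.3 reruns the model of 6.3.13.1 on each imputed data set. Neither section gives its own fallback, so the one in 6.3.13.1 appears to carry over.

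**The concern.** For four visits an unstructured covariance has 10 parameters and compound symmetry has 2. The single step from one to the other removes every visit-specific variance. The Week 6 standard error would then come from a variance averaged over Weeks 2, 4, 6 and follow-up. Nothing in the stated model protects the Week 6 test if that average is wrong for Week 6.

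A fallback matters only when the main model has failed, and at that point it should not add an equal-variance assumption that can be avoided. The width of the primary interval is at stake, and with it the actual level of a test described as 5% two-sided. The trial is a pilot whose stated use is to estimate the effect size for later studies, so interval width matters even without a confirmatory claim.

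**Working it through.** The plan has no figure to reproduce. Protocol 10.1 and SAP 5 say that the sample size does not rest on a power calculation, and neither document gives a MADRS SD, a between-visit correlation or a dropout rate.

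**Inputs from the documents**
- 60 patients per arm, three arms (Protocol synopsis).
- Four modelled visits, 4 to 7, with Week 6 (Visit 6) primary (SAP 6.3.13.1).
- Two-sided 5% level (SAP 6.3.2).

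**Assumed inputs**
- SDs of the baseline-adjusted change score at Visits 4/5/6/7. A range is shown because the documents give none.

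**Formulas (complete data)**
- True Week 6 SE = SD6 × sqrt(2/60) = 0.1826 × SD6.
- CS SE = sqrt(mean of the four visit variances) × sqrt(2/60).
- Ratio R = CS SE / true SE = sqrt(mean visit variance / Week 6 variance).
- Actual two-sided type I error = 2 × (1 − Φ(1.96 × R)).

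Worked example, SDs 6/8/10/10: mean variance = (36 + 64 + 100 + 100)/4 = 75, so R = sqrt(75/100) = 0.866. The true SE is 1.826 and the CS SE is 1.581. Type I error = 2 × (1 − Φ(1.697)) = 0.090.

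| Assumed SDs, Visits 4/5/6/7 | Mean variance / Week 6 variance | R | Week 6 SE under CS | Type I error |
|---|---|---|---|---|
| 8/9/9.5/9.5 | 81.38 / 90.25 | 0.950 | 5.0% too small | 0.063 |
| 7/8.5/9/9 | 70.81 / 81 | 0.935 | 6.5% too small | 0.067 |
| 6/7.5/8.5/9 | 61.38 / 72.25 | 0.922 | 7.8% too small | 0.071 |
| 7/8.5/9.5/9.5 | 75.44 / 90.25 | 0.914 | 8.6% too small | 0.073 |
| 5/7/9/10 | 63.75 / 81 | 0.887 | 11.3% too small | 0.082 |
| 6/8/10/10 | 75 / 100 | 0.866 | 13.4% too small | 0.090 |
| 8/8/8/8 | 64 / 64 | 1.000 | correct | 0.050 |
| 8/8.5/9/11 | 84.56 / 81 | 1.022 | 2.2% too large | 0.045 |
| 10/9/8/8 | 77.25 / 64 | 1.099 | 9.9% too large | 0.031 |
| 8/8/8/11 | 78.25 / 64 | 1.106 | 10.6% too large | 0.030 |

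**Simulation check.** The SAP mean model was fitted by REML with CS in 1,500 simulated trials per scenario, with 60 per arm, AR(1) correlation 0.7, completely random dropout and a normal critical value. All of these settings except the arm size are assumptions.

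| SDs | R, 0% / 5% dropout per visit | Type I error, 0% / 5% |
|---|---|---|
| 6/7.5/8.5/9 | 0.94 / 0.92 | 0.064 / 0.073 |
| 5/7/9/10 | 0.87 / 0.88 | 0.085 / 0.085 |
| 8/8/8/8 | 1.01 / 1.00 | 0.047 / 0.050 |
| 8/8/8/11 | 1.10 / 1.08 | 0.031 / 0.037 |
| 10/9/8/8 | 1.11 / 1.09 | 0.037 / 0.035 |

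The simulation agrees with the closed form in direction and size.

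**Role of the follow-up visit.** Take 7/8.5/9.5/9.5 and change only Visit 7. At 10.5, R is 0.944 and type I error 0.064. At 11.5 they are 0.976 and 0.056. A wider follow-up visit can therefore offset most of the understatement.

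**The case against.** **Direction.** A reader might infer that CS makes the Week 6 standard error too small. There is an argument for that. The outcome is change from baseline with baseline as covariate, so even if raw-score variance is constant, residual variance grows as correlation with baseline decays. Assumed baseline correlations of 0.6/0.45/0.35/0.3 give residual variances proportional to 0.64, 0.7975, 0.8775 and 0.91, hence R = 0.959 and type I error 0.060. The HAM-D entry criteria may also narrow severity at baseline and let scores spread later. But the documents report no visit SD and do not say how variance is expected to change, and the pooled variance includes an off-treatment visit. The table has plausible patterns on both sides of R = 1. The objection stands: only a conditional statement about direction is supported.

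**Trigger.** Failure of an unstructured fit is unlikely with four visits and about 180 patients. A reader might infer that repeated fits to imputed data make it more likely. They do not: SAP 6.3.13.3 expects fewer than 10 imputations, and the imputation fills in the missing visits, which makes the fit easier. The documents also give no evidence that the discrete CGI-S would fail. This stands and lowers the priority.

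**Restrictiveness.** CS is not the most restrictive structure available. AR(1) also has two parameters, and independence is simpler still. The relevant defect is the loss of visit-specific variances.

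**Stakes.** This is a pilot, and SAP 6.3.2 makes no multiplicity adjustment over the two dose comparisons, so strict error control is not claimed. Visit SDs (Table 14.2.2.1) and model variance terms (Table 14.2.2.4) would also show unequal variances after the fact. Both points stand as mitigation. Neither supplies a sound pre-specified analysis.

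**Sandwich errors.** Empirical standard errors correct the variance but do not repair bias in the estimate from a wrong covariance when data are missing at random, which SAP 6.3.4 assumes. This stands and determines the order of the fix.

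**Conclusion.** The point holds as a conditional one. If the fallback is used, CS may misstate the Week 6 standard error in either direction. It is about 5 to 13% too small (type I error about 6 to 9%) under the assumed SDs that rise to Week 6, and correct under equal SDs. It is about 10% too large (type I error about 3%) under the falling or much-wider-follow-up patterns tried. These sizes rest wholly on assumed SDs and, in the closed form, on complete data. The documents do not support saying that the standard error will be too small, or that the fallback is likely to be reached. That it is unlikely to be reached is a judgement from the number of visits and patients. This is a low-priority improvement that is worth making because it costs almost nothing.

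**What to change.** Replace the CS sentence in SAP 6.3.13.1 with wording such as: *If the unstructured model does not converge, the following structures will be tried in order and the first that converges will be used: heterogeneous Toeplitz, ARH(1), heterogeneous compound symmetry. If none converges, compound symmetry will be used with empirical (sandwich) standard errors. The same rule applies to the MMRMs for CGI-S, HAM-A and SDQ and to those fitted to the imputed data sets.*

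Each of the first three structures has its own Week 6 variance, so the list deals with misstatement in either direction. It changes nothing if the unstructured model converges.

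The cost is one short SAP edit and a few extra lines of code. The downside arises only at the last step: with plain CS and empirical errors the Kenward-Roger adjustment is lost, and the sandwich does not cure bias from a misspecified covariance under missing at random. For that reason the heterogeneous structures come first.
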